4 PHARMACOKINETIC ANALYSES

4.1 General Considerations

Subject characteristics will be summarized overall and by dose group. PK parameters determined by noncompartmental approaches will be summarized by dose group. Statistics include the arithmetic mean, geometric mean, standard deviation (SD), coefficient of variation (CV), minimum (min), maximum (max), and median.

4.2 PK Analysis Population

All subjects who receive active study drug and have at least 1 measured oxfendazole concentration at a scheduled PK time point after start of dosing are eligible for the PK population. If any subjects are found to be noncompliant with respect to dosing, have incomplete data, or an event that is likely to affect PK, a decision will be made on a case-by-case basis as to their inclusion in the population. Subjects excluded from the PK analyses and their reasons for exclusion will be denoted and detailed in the PKAR.

4.3 Demographics and Other Subject Characteristics

The following variables will be summarized for the PK analysis population:

- Demographic variables: gender, age, race, and ethnicity.
- Physical characteristics: height and weight recorded at the PK dosing visits or carried forward from a previous study visit.
- Clinical laboratory parameters: Creatinine, AST, ALT

4.4 Summary of Pharmacokinetic Sampling and Sample Properties

4.4.1 Handling of Special Cases in Analyses

Key protocol violations and deviations related to PK sample collection or storage that could potentially impact PK results will be summarized. Samples with bioanalytical errors reported by the laboratory will be excluded. Collection times of samples missing the actual collection time will be imputed using the nominal collection time. Such samples will be identified in the PKAR.

4.5 Interim Pharmacokinetic Analyses

This study is a rising dose safety/tolerance study in which plasma is collected for analysis of oxfendazole, fenbendazole and sulfone levels. The primary aim is to determine to what level single doses can be increased without causing limiting toxicity in normal volunteers.

In order to assess safety of rising dose levels and to facilitate planning for future product development activities without jeopardizing data integrity for this trial, pharmacokinetic data will be entered into the trial database as they become available and reviewed after each dose group. After PK data for a cohort is complete, locked and finalized, group-level results will be distributed to the study team. These data may be distributed in limited fashion such as grant applications.

Subject baseline characteristics will be summarized and presented by Dose group. Dose group-level summary statistics as well as line plots for of oxfendazole, fenbendazole and sulfone levels will be presented.

All PK parameters will be presented by group and specimen type. No individual subject summaries will be presented in interim pharmacokinetic report.

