PROTOCOL SYNOPSIS

Title of the Trial	A Randomized, Double-Blind Placebo-Controlled Phase I Trial Evaluating the Safety and Pharmacokinetics of Oxfendazole
Investigators	[name] University of Iowa University of Iowa Hospitals and Clinics [name] [contact] [contact] E-mail: [contact]
Trial Center	The University of Iowa
Trial Period	First Subject First Visit: 17 November 2014 Last Subject Last Visit: October 2015 (anticipated)
Development Phase	Phase I
Objectives	
Primary:
 
 • Assess the safety and tolerability of oxfendazole in healthy adults. 
Secondary:
 
 • Assess the pharmacokinetic profile of oxfendazole • Assess the metabolism of oxfendazole
Sample Size	70 (10 subjects in each of 7 dose groups)
Investigational product	Single oral dose of an aqueous suspension of oxfendazole, a benzimidazole carbamate antiparasitic drug.
Duration of Follow-up	2 weeks
Endpoints for Analysis	
Primary Endpoint The rate of adverse events (AEs) related to oxfendazole within 14 days of receipt of a single oral dose.
 
Secondary Endpoints Plasma C_{max}, T_{max}, AUC, t_{1/2} of oxfendazole for each dosage group. Plasma and urine concentrations of oxfendazole fenbendazole and oxfendazole sulfone at time points specified in Appendix A Schedule of Events and described in Section 4 Study Design relative to oral dosing.

PHARMACOKINETIC ANALYSIS PLAN SIGNATURE PAGE:

Sponsor: Division of Microbiology and Diseases
National Institute of Allergy and Infectious Diseases
National Institutes of Health

Protocol Number: **DMID 12-0053**

Study Title: A Randomized, Double-Blind Placebo-Controlled Phase I Trial Evaluating
the Safety and Pharmacokinetics of Oxfendazole

Principal Investigator: [name].

Signed:

Date:

Title:

DMID Scientific Lead: [name].

Signed:

Date:

Title:

The Emmes Corporation: [name]

Signed:

Date:

Title: Statistician

TABLE OF CONTENTS

	Page
PROTOCOL SYNOPSIS	iii
PHARMACOKINETIC ANALYSIS PLAN SIGNATURE PAGE:	iv
TABLE OF CONTENTS.....	v
LISTING OF ABBREVIATIONS.....	1
1 PREFACE.....	3
2 INTRODUCTION	3
2.1 Purpose of the Pharmacokinetic Analyses.....	4
3 STUDY DESIGN, OBJECTIVES AND ENDPOINTS	4
3.1 Study Design.....	4
3.2 Study Objectives (Pharmacokinetic Only)	5
3.3 Study Outcome Measures (Pharmacokinetic Only)	5
4 PHARMACOKINETIC ANALYSES	5
4.1 General Considerations.....	5
4.2 PK Analysis Population.....	5

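### The interim PK report's baseline table (SAP 4.5) names no population; on its most natural, active-drug-only reading it lets holders of a cohort's records deduce the two placebo subjects

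*SAP*

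**What the plan says.** SAP 4.5 plans a PK review after each dose group. Once a cohort's PK data are locked, "group-level results will be distributed to the study team". The interim report includes a baseline table: "Subject baseline characteristics will be summarized and presented by Dose group". The stated safeguard is: "No individual subject summaries will be presented in interim pharmacokinetic report". One purpose given for the review is "In order to assess safety of rising dose levels".

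SAP 4.5 does not name the population for the baseline table. Three other places in the SAP bear on it:

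- SAP 4.3 introduces the baseline variables with "The following variables will be summarized for the PK analysis population".
- SAP 4.2 defines that population as "All subjects who receive active study drug and have at least 1 measured oxfendazole concentration" at a scheduled time after dosing.
- Exhibit 1 has one column per dose group with its N, a row for dose in mg, and no placebo column.

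The SAP synopsis points the other way: it counts 10 subjects in each dose group, which includes placebo.

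SAP 4.2 also says "Subjects excluded from the PK analyses and their reasons for exclusion will be denoted and detailed in the PKAR". SAP 2.1 uses the abbreviation PKAR for the interim report too.

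On the protocol side, section 10.3.2 lets group-level PK means and SDs go to the study team and mentions no baseline table. Sections 8.5 and 8.6.2 have the SRC, made up of the Principal Investigator and the Independent Safety Monitor, review blinded safety data for each completed cohort.

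**The concern.** Group-level reporting normally protects a blind because no single subject can be picked out. Here the group is 8 of a known 10, and some likely recipients hold the other side of the subtraction. Site staff and the Principal Investigator have every subject's age, height and weight. A summary of the 8 who received drug tells them, by difference, about the 2 who did not.

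The primary endpoint (protocol 3.2.1) is the rate of AEs related to oxfendazole, so it rests on relatedness judgments. Under protocol 8.5 the SRC's continuation rule counts product-related grade 2 and grade 3 AEs, and failure of its two members to agree on relatedness is itself a halting trigger. If one member could know the placebo pair when those judgments are made, the blinding of the review would be nominal.

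**Working it through.** **Allocation (protocol 4, SAP 3.1).** 7 cohorts × 8 drug = 56 and 7 × 2 placebo = 14, total 70, as stated.

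**Candidate placebo pairs in a cohort.** 10 × 9 / 2 = 45. The sentinel rule (one drug, one placebo) makes one placebo subject one of the 2 sentinels and the other one of the remaining 8: 2 × 8 = 16. A blind guess at the pair is right 1/45 = 2.2% or 1/16 = 6.25% of the time.

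**Why a mean gives the pair away.** SAP 5 reports means to one decimal more than the data. If values are recorded to unit *u*, the mean of 8 is known to within 0.05*u*, so their total is known to within 8 × 0.05*u* = 0.4*u*. That is less than half a unit, so the exact total is recovered. Subtracting it from the total of all 10 gives the exact sum for the two missing subjects. Age, height and weight give three such sums, and the pair is hidden only if another pair ties on all three.

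**How often that happens (simulation; the distributions are assumptions, not in the documents).** Weight mean 80 kg, SD 10 to 18; height mean 177 cm (men) or 164 cm (women), SD 7; age uniform over 18–45 or 18–30; 70–100% male; height and weight recorded to 1 or 0.1 unit. All 8 active subjects are in the table.

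| Information used | Pair identified, 16 candidates | Pair identified, 45 candidates |
|---|---|---|
| Three means, SAP 5 precision | 99.9–100% | 99.5–100% |
| Three means, rounded to whole units | about 75–93% | about 50–83% |
| Mean weight alone (to 0.1 kg; 70% male, BMI 18–35) | 98.8% | 91.5% |
| Sex count alone | under 1% | under 1% |

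The lower whole-unit figures come from the narrower age range. With the full Exhibit 1 statistics, the pair was unique in all 400 simulated cohorts, with or without the sentinel rule.

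**Minimum and maximum.** No calculation is needed if a placebo subject is the cohort's sole oldest, youngest, tallest, shortest, heaviest or lightest: that value is simply absent from the table. For one variable without ties, the chance that neither placebo subject is an extreme is (8 × 7 / 2) / 45 = 28/45 = 62.2%. For three independent variables, the chance that at least one placebo subject is exposed is 1 − 0.622³ = 76%. With ties and rounding, the simulations gave about 68–76%.

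**One active subject left out of the PK population (N = 7 shown).** The three missing subjects were identified in 99.6–100% of cohorts. That leaves 3 candidate pairs, or 2 with the sentinel rule. If the interim report also names the excluded subject, as SAP 4.2 allows, 1 remains.

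**Check of the alternative remedy (table of all 10).** Without the dose row, the table does not depend on assignment, so all 16 or 45 pairs stay possible. If the dose row is kept with placebo entered as 0 mg, the pair is still identified (16 candidates) in 44–66% of cohorts at 0.5 mg/kg and in 70–98% at 7.5 or 60 mg/kg.

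**The case against.** **The population is an inference.** This stands. SAP 4.5 is silent, the synopsis counts 10 per group, and SAP 1 allows minor changes to table design. If all 10 were meant and no dose row were shown, there would be no leak. But SAP 4.2, SAP 4.3 and the Exhibit 1 shell all favour the active-only reading, and on either reading the population should be named.

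**A reader might infer that the SAP breaches the protocol.** The documents do not support that. Protocol 10.3.2 says what may be distributed and does not make the list exclusive. Protocol 13.11 lets the sponsor generate interim statistical reports as it sees fit. The baseline table goes beyond what 10.3.2 describes; it is not forbidden.

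**The window is narrow.** This also stands. Protocol 7.2.2 ships samples only after the cohort is completed, and results go out only after PK lock. AEs are documented through about 14 days (protocol 8.3), so most relatedness calls will already have been made. If the SRC meets before release, its decision for that cohort is untouched. However, no passage sets the order, and AEs are followed to resolution beyond the reporting period (protocol 8.4), so some judgments can come later.

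**Someone has to try, and other checks exist.** The percentages measure whether the deduction can be done, not whether anyone would do it. Disagreement within the SRC goes to the Safety Monitoring Committee, and severity is graded by table. Both limit the effect. Outside readers, such as those of a grant application, lack the individual records.

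**The table is not the only possible route.** PK data enter the trial database as they become available, and the documents do not say who can see subject-level concentrations. Changing the table closes this route only.

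**Conclusion.** The point holds as a gap in SAP 4.5: a by-dose-group baseline table goes to an undefined study team after each cohort with no population named. On the most natural reading, that table identifies the placebo pair to anyone holding the cohort's records, in at least 99.5% of simulated cohorts from three means at the SAP's own precision. That figure assumes the distributions listed above, all 8 active subjects in the table, and a recipient with all 10 records. The mechanism itself, exact sums recovered from the rounded means, does not depend on those distributions.

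It would be tempting to conclude that the SRC will be unblinded or that the primary endpoint is biased. The documents show neither. The first depends on an unstated release order and on someone making the deduction; the second would also need relatedness calls to change as a result. This is an inexpensive improvement worth making, not a flaw that invalidates the design.

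**What to change.** In SAP 4.5, hold the baseline table for the final report, and in SAP 4.2 hold the list of excluded subjects for the final PKAR. The active-only Exhibit 1 can then be used unchanged.

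If an interim baseline table is wanted, state that it covers all 10 randomised subjects in the cohort and leave out the dose row, since keeping that row with placebo as 0 mg still reveals assignment.

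The cost is a short SAP edit. Under the first option, interim readers lose, until the final report, the weight and dose context that helps interpret PK under weight-based dosing. Under the second, the table describes two people per cohort who are not in the PK population. The interim concentration and parameter summaries are unaffected either way.

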4.6 Primary Pharmacokinetic Analysis

4.6.1 Concentration Summaries

Dose group-level summary plots will be produced by plotting plasma concentrations (mean \pm SD) versus nominal time to explore average trends and variability. Dose group-level summary plots of the amount excreted in urine will be produced by plotting the cumulative amount excreted in each collection interval versus the midpoint of the collection interval.

4.6.2 Pharmacokinetic Parameters

Pharmacokinetic parameters will be calculated using actual post-dose time. All PK parameters will also be summarized by dose group and specimen type using descriptive statistics. Additionally, subject-level PK parameters will be presented by subject in data listings in the final PKAR.

The following parameters will be calculated from the concentration-time profiles:

Maximum plasma concentration (C_{max}) is defined as: the maximum observed drug concentration in blood plasma for a particular dose interval.

Time of maximum plasma concentration (T_{max}) is defined as: the time at which the maximum plasma concentration occurs.

AUC_{0-t} is defined as: the area under the concentration-time curve from administration (time 0) to the time of the last quantifiable concentration at time =t.

The following parameters will be estimated when the elimination rate constant is estimable:

Elimination rate constant (λ_z) is defined as: the first-order rate constant describing rate of elimination from plasma.

Elimination half-life ($t_{1/2}$) is defined as: the time required for a drug concentration to be reduced by half during the elimination phase. The terminal half-life will be estimated by $\ln(2)$ divided by λ_z .

$AUC_{0-\infty}$ is defined as: the total area under the concentration-time curve and is computed by adding AUC_{0-t} to an extrapolated value equal to the last measured concentration greater than limits of quantitation divided by λ_z and will be calculated using

$$AUC_{0-\infty} = AUC_{0-t} + \frac{C_{tf}}{\lambda_z},$$

where C_{tf} is the last measurable concentration \geq LLOQ

Oral clearance (CL/F) is calculated as: the dose divided by the $AUC_{0-\infty}$.

Apparent volume of distribution (V_z/F) is defined as: the theoretical volume that the total amount of administered drug would occupy to provide the same concentration as it currently is in blood plasma divided by the bioavailability.

$$V_z / F = \frac{Dose}{\lambda_z \times AUC_{0-\infty}}$$

Amount of drug excreted in urine (Ae) is defined as: the cumulative amount of drug excreted in urine. Ae will be used to calculate the fraction of dose excreted in urine (fe) and estimate renal clearance (CL_R).

Additional parameters may be estimated, if appropriate.

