1 PREFACE

The Statistical Analysis Plan (SAP) for “DMID Protocol 12-0053: A Randomized, Double-Blind Placebo-Controlled Phase I Trial Evaluating the Safety and Pharmacokinetics of Oxfendazole” describes and expands upon the statistical information presented in the protocol.

This document describes all planned pharmacokinetic analyses, and provides reasons and justifications for these analyses as well as all planned sample tables, listings and figures. Regarding the final analysis and final integrated Clinical/Statistical Report (CSR), this SAP follows the International Conference on Harmonisation of Technical Requirements for Registration of Pharmaceuticals for Human Use (ICH) Guidelines, as indicated in Topic E3 (Structure and Content of Clinical Study Reports), and more generally is consistent with Topic E8 (General Considerations for Clinical Trials) and Topic E9 (Statistical Principles for Clinical Trials). The structure and content of the SAP provides sufficient detail to meet the requirements identified by the FDA and ICH, while all work planned and reported for this SAP will follow internationally accepted guidelines published by the American Statistical Association and the Royal Statistical Society for statistical practice.

This document contains four sections: (1) a review of the study design, (2) general statistical considerations, (3) comprehensive statistical analysis methods for pharmacokinetic outcomes, and (4) a list of proposed tables and figures. Any deviation from this statistical plan will be described and justified in protocol amendments and/or in the final study report, as appropriate. The reader of this SAP is encouraged to also review the clinical protocol for details on conduct of the study and the operational aspects of clinical assessments.

Some minor modifications may be necessary to the planned design of tables, figures, and listings to accommodate data collected during the actual study conduct.

IMPORTANT NOTES:

Tables, indicated by footnote, presented in this statistical analysis plan will be presented by dose group.

This SAP relies on simulated (fake) sample data to illustrate the statistical methods, tables, and graphical displays that will be used in analyzing the study data. These simulated data are for illustrative purposes only and no inferences should be drawn regarding pharmacokinetic profiles. Appropriate scales and units will be added to all figures for the final analysis.

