3 STUDY DESIGN, OBJECTIVES AND ENDPOINTS

3.1 Study Design

This Phase I study is a randomized, double-blind, placebo-controlled evaluation of the safety and PK of escalating single oral doses of oxfendazole (0.5, 1, 3, 7.5, 15, 30, 60 mg/kg) in healthy volunteers. Each cohort will comprise 10 volunteers (8 drug, 2 placebo). Subjects will be monitored for 2 weeks after dosing, including monitoring the PK and metabolism of oxfendazole in blood and urine. Projected duration of subject participation will be 3-6 weeks of face to face visits, including the screening period. It is anticipated that it will take 18 months to finish the study.

Two sentinel subjects (one randomized to receive study drug and the other to receive placebo) will be dosed and monitored 48 hours for adverse events prior to enrolling the remaining subjects in each cohort. If no drug-related serious adverse event or laboratory grade 3 study drug related events are observed within the 48 hour period, the remainder of the cohort will proceed with dosing. Each new cohort will be dosed only after the 2-week safety data for the preceding group have been analyzed. A Safety Review Committee (SRC) composed of the Protocol Principal Investigator and Independent Safety Monitor will review blinded safety data for the completed cohort. If a clinically significant AE is observed that is possibly drug related, the SRC will determine if an ad hoc SMC meeting should be called. Up to 70 volunteers (56 drug, 14 placebo) will complete the study. The Safety Monitoring Committee (SMC) will review the safety data either when or if the final dose is reached.

Sample Collection:

Blood and urine will be obtained for PK analysis. Blood samples for PK analysis are collected at 14 time points: baseline (prior to product administration); 1, 2, 4, 6, 8, 10, 12 (all times have a window of +/- 15 minutes except the 10 and 12 hour samples which have a window of +/- 30 minutes), and 24 (+8) hours; and Days 3, 4, 6, 8 and 15 after dosing. Urine for oxfendazole, metabolites, and creatinine will be

collected. Urine for PK analysis will be collected at baseline (prior to product administration) and for the first 24 hours after product administration with specific collections times of urine for oxfendazole, 0-4, 4-8, 8-12, 12-24. Spot urine samples will be collected at 24 (+ 8 hrs) and on Day 3 after dosing.

Samples for PK studies will be processed at [name] laboratory at the University of Iowa.

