Line Plots of Mean Sulfone (Plasma) Concentration by Nominal Time***

*Error bars give +/- standard deviation.

**EXHIBIT 10:
Summary Statistics for Cumulative Amount of Oxfendazole
Excreted Unchanged in Urine by Nominal Time***

	Pre-Dose	0-4 hours	4-8 hours	8-12 hours	12-24 hours
Statistic					
N					
Mean					
SD					
Min					
Median					
Max					

* This table will be repeated for each dose group.
Subject level data is presented in Listing 2.

**EXHIBIT 11:
Summary Statistics for Cumulative Amount of Fenbendazole
Excreted Unchanged in Urine by Nominal Time***

	Pre-Dose	0-4 hours	4-8 hours	8-12 hours	12-24 hours
Statistic					
N					
Mean					
SD					
Min					
Median					
Max					

[figure not shown]
* This table will be repeated for each dose group.
Subject level data is presented in Listing 2.

EXHIBIT 12:
**Summary Statistics for Cumulative Amount of Sulfone
Excreted Unchanged Urine by Nominal Time***

	Pre-Dose	0-4 hours	4-8 hours	8-12 hours	12-24 hours
Statistic					
N					
Mean					
SD					
Min					
Median					
Max					

[figure not shown]
This table will be repeated for each dose group.
Subject level data is presented in Listing 2.

**EXHIBIT 13:
Cumulative Amount of Oxfedazole
Excreted Unchanged in Urine by Nominal Time***

[figure not shown]
This figure will be repeated for each dose group.

EXHIBIT 14:
Cumulative Amount of Fenbendazole
Excreted in Urine by Nominal Time*

This figure will be repeated for each dose group.

EXHIBIT 15:
**Summary Statistics for Cumulative Amount of Sulfone
Excreted in Urine by Nominal Time***

This figure will be repeated for each dose group.

**EXHIBIT 16:
Individual and Summary Statistics for Oxfedazole Noncompartmental PK Parameters***

Subject ID	AUC_{0-t} (ng·hr/mL)	AUC_{0-∞} (ng·hr/mL)	T_{max} (hr)	C_{max} (ng/mL)	N for λ_z	λ_z (hr ⁻¹)	t_{1/2} (hr)	CL/F (L/hr)	V_z/F (L)	CL_R (L/hr)	fe
001											
002											
003											
N											
Mean											
SD											
Min											
Max											
CV %											
GM											

* This table will be repeated for each dose group.

LLOQ = 2 ng/ml

LLOD = 1 ng/ml

N= number of time points used to calculate λ_z

EXHIBIT 17:
Individual and Summary Statistics for Fenbendazole Noncompartmental PK Parameters*

Subject ID	AUC_{0-t} (ng·hr/mL)	AUC_{0-∞} (ng·hr/mL)	T_{max} (hr)	C_{max} (ng/mL)	N for λ_z	λ_z (hr ⁻¹)	t_{1/2} (hr)	CL/F (L/hr)	V_z/F (L)	CL_R (L/hr)	fe
001											
002											
003											
N											
Mean											
SD											
Min											

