Max											
CV %											
GM											

* This table will be repeated for each dose group.

LLOQ = 2 ng/ml

LLOD = 1 ng/ml

N= number of time points used to calculate λ_z

EXHIBIT 18:
Individual and Summary Statistics for Sulfone Noncompartmental PK Parameters*

Subject ID	AUC_{0-t} (ng·hr/mL)	AUC_{0-∞} (ng·hr/mL)	T_{max} (hr)	C_{max} (ng/mL)	N for λ_z	λ_z (hr ⁻¹)	t_{1/2} (hr)	CL/F (L/hr)	V_z/F (L)	CL_R (L/hr)	fe
001											
002											
003											
N											
Mean											
SD											
Min											
Max											
CV %											
GM											

* This table will be repeated for each dose group.

LLOQ = 2 ng/ml

LLOD = 1 ng/ml

N= number of time points used to calculate λ_z

LISTING 1:
Subject Level Demographic and Baseline Characteristics

Dose Group	Subject ID	Dose (mg)	Sex	Age (Years)	Weight (kg)	Height (cm)

LISTING 2:
Subject Level Amount Excreted in Urine and Urine Concentrations by Treatment Group and Analyte

Dose Group	Subject ID	Visit Number (Study Day)	Scheduled Collection Interval (hr)	Actual Collection Interval (hr)	Start Date (Time) of Urine Collection	Stop Date (Time) of Urine Collection	Collected Urine Volume (mL)	Date (Time) of Sample Collection	Oxfendazole		Fenbendazole		Sulfone	
									Concentration (ng/mL)	Amount Excreted (mg)	Concentration (ng/mL)	Amount Excreted (mg)	Concentration (ng/mL)	Amount Excreted (mg)

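### SAP Exhibits 17 and 18 report CL/F and Vz/F for two metabolites, although SAP 4.6.2 defines both only from the administered oxfendazole dose

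*SAP*

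**What the plan says.** **Plasma parameters.** The SAP synopsis describes the product as "Single oral dose of an aqueous suspension of oxfendazole, a benzimidazole carbamate antiparasitic drug"; no metabolite is dosed. SAP 4.6.2 states "Oral clearance (CL/F) is calculated as: the dose divided by the" AUC to infinity, and gives Vz/F as dose over the product of λz and that AUC, tying the volume to the drug that was administered. There is no separate definition for a metabolite, no fraction formed and no molar conversion.

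Exhibit 17 is titled "Individual and Summary Statistics for Fenbendazole Noncompartmental PK Parameters" and Exhibit 18 "Individual and Summary Statistics for Sulfone Noncompartmental PK Parameters". Both repeat the columns of Exhibit 16 (oxfendazole), including CL/F in L/hr and Vz/F in L.

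Protocol section 10.4 plans the non-compartmental parameters for oxfendazole only. The secondary endpoints (protocol 3.2.2, SAP 3.3) are Cmax, Tmax, AUC and half-life of oxfendazole, plus concentrations of all three analytes.

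**Urine.** SAP 4.6.1 plans group plots made by "plotting the cumulative amount excreted in each collection interval versus the midpoint of the collection interval". SAP 4.6.2 states: "Amount of drug excreted in urine (Ae) is defined as: the cumulative amount of drug excreted in urine". SAP 3.1 gives "specific collections times of urine for oxfendazole, 0-4, 4-8, 8-12, 12-24" hours. Exhibits 10 to 15 have *cumulative amount* in their titles, but the columns of Exhibits 10 to 12 are headed by separate intervals (0-4, 4-8, 8-12, 12-24 hours). Listing 2 records the amount excreted by collection interval.

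**The concern.** Dose over AUC estimates CL/F when the analyte is the substance that was dosed. For a metabolite, the amount entering plasma is not the dose but an unknown share of it, so the quotient mixes metabolite clearance with the extent of formation. A reader of Exhibits 17 and 18 could take the columns as the clearance and volume of fenbendazole and sulfone.

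Metabolism is a stated secondary objective, so these tables will be read for that purpose. SAP 4.5 also has PK parameters summarised by group in interim reports, with limited outside distribution possible, so a mislabelled value could circulate before the final report.

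The urine wording raises a smaller question. A running total is known only at the end of an interval, whereas a midpoint suits a per-interval quantity. The SAP does not say consistently which one it means.

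**Working it through.** The plan states no figure to reproduce. The check is algebra on the SAP's formulas, followed by illustration with assumed values, because the documents give no fraction metabolised, bioavailability or half-life.

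**Notation.** F is the fraction of the oxfendazole dose reaching plasma as oxfendazole. fm is the fraction of that converted irreversibly to the metabolite. fp is the fraction of the dose that forms metabolite during first pass and reaches plasma as such. CLm, Vm and km = CLm/Vm belong to the metabolite; kp is the parent's elimination rate constant. Dose and AUC are taken on the same molar basis.

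**1. CL/F, formation after absorption only (fp = 0).**
- AUCm = F × fm × Dose / CLm, so Dose/AUCm = CLm/(F × fm).
- Relative to CLm/F the factor is 1/fm. F cancels, because the label already declares it.
- Assumed fm = 1: factor 1. fm = 0.5: 1/0.5 = 2. fm = 0.1: 1/0.1 = 10.

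**2. CL/F with first-pass formation.** The factor becomes F/(fm × F + fp). With assumed F = 0.5:

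| fm | fp = 0 | fp = 0.1 | fp = 0.25 |
|---|---|---|---|
| 0.5 | 0.5/0.25 = 2.0 | 0.5/0.35 = 1.43 | 0.5/0.50 = 1.0 |
| 0.1 | 0.5/0.05 = 10 | 0.5/0.15 = 3.33 | 0.5/0.30 = 1.67 |

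**3. Vz/F (fp = 0).**
- The SAP formula gives CLm/(F × fm × λz). Relative to Vm/F the factor is km/(fm × λz).
- If the metabolite is eliminated more slowly than the parent, λz = km and the factor is again 1/fm.
- If it is eliminated faster, its terminal slope follows the parent, λz = kp, and the factor is (parent half-life / metabolite half-life)/fm.
- With assumed fm = 0.5 and parent half-life 12 h: metabolite half-life 24 h gives 1/0.5 = 2; 6 h gives (12/6)/0.5 = 4; 3 h gives (12/3)/0.5 = 8.

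**4. Mass basis.** At fm = 0.25, F = 1 and an assumed CLm of 20 L/h, the column reads 20/0.25 = 80 L/h. An assumed metabolite-to-parent molar-mass ratio of 0.95 or 1.05 moves it to 80/0.95 = 84.2 or 80/1.05 = 76.2 L/h, about 5%. This is small beside the fraction formed, but it should be stated.

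**5. Identifiability.** There is no intravenous arm and no arm in which a metabolite is dosed, so plasma data cannot separate CLm from the fraction formed. Urine recovers only what the kidney excretes, and timed collection ends at 24 h, so it does not supply the fraction either.

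**6. Urine wording, side by side.**
- For a running total: the definition of Ae in 4.6.2 and the titles of Exhibits 10 to 15.
- For a within-interval amount: the phrase in 4.6.1 about each collection interval, the midpoint axis, the column heads of Exhibits 10 to 12 (a running total would be headed 0-4, 0-8, 0-12, 0-24), and Listing 2.
- The interval ends are 4, 8, 12 and 24 h and the midpoints 2, 6, 10 and 18 h. The choice therefore moves the plotted points by 2, 2, 2 and 6 h.

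**The case against.** The strongest defence of the columns is that the SAP's abbreviation list defines F only as bioavailability. If F is read as the fraction of the dose reaching plasma as the listed analyte, dose over AUC equals CL/F for that analyte by construction. Oxfendazole CL/F also carries an unknown F, and 4.6.2 already calls the volume apparent. But the SAP nowhere adopts an analyte-specific F, and that reading does not rescue Vz/F when the metabolite's slope follows the parent. With fm absorbed into F, the factor at a parent half-life of 12 h is still 12/6 = 2 or 12/3 = 4 for metabolite half-lives of 6 or 3 h.

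The Preface says "Some minor modifications may be necessary to the planned design of tables, figures, and listings to accommodate data collected during the actual study conduct". That allowance is for fitting shells to the data obtained; it does not supply a missing definition.

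It is also fair that the consequence is small. Metabolite AUC and the dose are both reported, so a careful reader could reconstruct what the columns contain. This stands and limits the weight of the point.

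On urine, a reader might infer that excretion will be drawn 2 to 6 hours too early. The documents do not support that as a shown error. It follows only if the plotted quantity is a running total, and the interval wording, the column heads and Listing 2 fit a per-interval amount equally well.

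**Conclusion.** The point on Exhibits 17 and 18 holds. Followed as written, the SAP produces metabolite columns labelled CL/F and Vz/F that are confounded by an unidentifiable fraction formed, and Vz/F may also carry the parent's terminal slope.

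The size cannot be computed from the documents. The factors of 1, 2 and 10 for CL/F rest on assumed fm, irreversible formation and no first-pass formation. A reader might infer that the columns are always badly inflated, but the illustrations include a factor of 1, so the error may be nil or large and the plan cannot tell which. The Vz/F figures depend in addition on assumed half-lives.

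The urine point is an internal inconsistency to clarify and no more.

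Both points concern descriptive PK reporting. No named endpoint, safety result or oxfendazole parameter changes.

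**What to change.** - **Exhibits 17 and 18:** delete the CL/F and Vz/F columns. This loses no endpoint and agrees with protocol 10.4. Alternatively, keep them under a label such as CLm/(F × fm), with a footnote that they are apparent values including the unknown fraction of the dose formed, and state the molar conversion of the oxfendazole dose.
- **SAP 4.6.1 and Exhibits 10 to 15:** state which urine quantity is meant. If it is a running total, plot it at the interval end (4, 8, 12, 24 h) and head the columns to match. If it is per interval, drop the word *cumulative* and keep the midpoint, preferably plotting excretion rate (amount divided by interval length), because the last interval is 12 h and the others are 4 h.

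The cost is SAP wording and table shells only. No new samples, assays or data are needed.
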